Skeletal muscle loss and impairment – prominent features of the aging process – lead to physical disability. There is plausible evidence that altering components of the diet, mainly *protein intake* and *acid/base balance*, may improve indices of muscle health in older adults and thus translate to a reduction in physical disability. A growing number of studies suggest that increasing protein intake using a whey protein supplement may benefit muscle health in older adults. However, a main concern is that high protein results in a large dietary acid load from the breakdown of protein to acidogenic byproducts, which could in turn promote muscle degradation particularly in older adults with age-related declines in renal excretion of acid. Thus, our hypothesis is that the balance between the amount of protein in the diet (anabolic component) and the net acid load of the diet (catabolic component) in part determines whether the diet as a whole has a net anabolic or catabolic effect on muscle. Preliminary data from our group have suggested that a daily potassium bicarbonate (KHCO₃) supplement improved lower extremity muscle power in postmenopausal women. Based on our preliminary data, we plan to conduct a randomized, double-blind, placebo-controlled, 2x2 factorial study in which underactive men and women age 65 and older on baseline lower protein diets will be enrolled. Participants will be assigned to one of four groups: either a whey protein supplement (to raise protein intake to 1.5 g/kg/d) with or without KHCO₃ 81 mmol/d or an isocaloric placebo supplement with or without KHCO₃ 81 mmol/d for 24 wks. The primary outcome is lower extremity muscle power at 24 weeks. Secondary outcomes are lower extremity muscle power at 12 weeks, knee extension strength/torque at 12 and 24 weeks, physical performance at 24 weeks, lean mass at 24 weeks, and 24-hr urinary nitrogen excretion adjusted for nitrogen intake at 24 weeks. Exploratory outcomes will include a measure of muscle mass – D₃-creatine dilution – and how it correlates with the older method – lean mass. Our central hypothesis is that higher protein intake and a neutralizing alkaline salt will improve muscle performance and mass, compared to their respective placebos, in older men and postmenopausal women. If successful, this research could result in a paradigm shift in dietary advice to older adults to reduce physical disability. As 1 in 5 US adults will be over age 65 by year 2040, a safe dietary intervention that reduces age-related musculoskeletal decline will be an important preventative health step for our aging society.

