Our 6-wk randomized, protein cross-over, controlled feeding pilot¹⁵ found that increasing dietary protein up to 1.5 g/kg/d and KHCO_3 at 90 mmol/d reduced by almost 50% the rise in UNi that accompanied a higher protein intake in both men and postmenopausal women suggesting a decrease in muscle breakdown. Our most recent trial²⁵ found better tolerability with an 81 mmol/d dose of KHCO_3 without compromising efficacy, thus making the 81 mmol/d dose more desirable in a longer-term study. *Based on our pilot data conducted under controlled feeding conditions, a plausible hypothesis that we aim to test in this larger study is that a high protein intake and KHCO_3 will enhance muscle power, endurance, physical performance and mass in an older sedentary population on lower protein intake.*

In this proposal, we plan to conduct a 24-wk, double-blind, randomized, placebo-controlled 2x2 factorial study in underactive women and men aged ≥ 65 yrs and on a ≤ 0.8 g/kg/d protein diet, to achieve the following specific aims:

Primary Aim: To test the effects of supplemental whey protein (to achieve 1.5 g/kg/d) and/or KHCO_3 81 mmol/d on lower extremity muscle power by double leg press at 24 wks;

Secondary Aims: To test the effects of supplemental whey protein (to achieve 1.5 g/kg/d) and/or KHCO_3 81 mmol/d on changes in:

- 2a) lower extremity muscle power at 12 wks;
- 2b) knee extension peak torque at 12 and 24 wks;
- 2c) handgrip strength at 24 wks;
- 2d) muscle mass as measured by appendicular non-fat non-bone lean mass by dual energy x-ray absorptiometry (DXA) at 24 wks;
- 2d) modified SPPB at 24 wks;
- 2e) 24h UNi excretion;

Exploratory Aims:

To test the individual and additive effects of supplemental whey protein (to achieve 1.5 g/kg/d) and/or KHCO₃ 81 mmol/d on 24-wk changes in muscle mass as measured by D₃-creatine dilution;

Background

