Risk of injury from testing of physical capacity is very low. The only risk expected to be associated with these tests is a risk of losing balance during the gait speed. The examiner will remain close to help volunteers who are unsteady.

D₃-Creatine Dilution

This is an oral dose of deuterium-labelled creatine (stable isotope) to determine total skeletal muscle mass via estimation of total body creatine pool size. Giving 60 mg of D₃-creatine has no known side effects.

Known Potential Benefits to Participants

This study is not designed to benefit individual participants. Screening lab results will be made available to the participants. If any adverse medical conditions are discovered during the study, participants will be notified in person or by telephone by the study physician/PI, [name]. If the adverse condition is mild, the participant will be referred to their doctor for an clinic evaluation. If the adverse condition is severe, the participant will be referred to urgent care or the emergency room.

Assessment of Potential Risks and Benefits

The risks incurred are minimal relative to the potential benefit of gaining information about one's health.

OBJECTIVES AND ENDPOINTS

We propose to conduct a 2x2 factorial design single center double-blind randomized controlled clinical trial. We plan to enroll 300 participants to obtain 120 completers. Each treatment arm will aim to include 30 participants.

Treatment Arms:

- Arm 1: Whey protein packet + KHCO₃ supplement
- Arm 2: Whey protein packet + placebo supplement
- Arm 3: Isocaloric placebo packet + KHCO₃ supplement
- Arm 4: Isocaloric placebo packet + placebo supplement

The primary outcome is the lower extremity muscle power at 24 weeks as measured by the double leg press. Secondary outcomes are lower extremity power at 12 weeks, knee extension torque at 12 and 24 weeks, and handgrip strength, physical performance as measured by the modified SPPB, appendicular non-bone non-fat lean tissue mass as measured by whole body DXA scan, and 24-h urinary nitrogen excretion adjusted for nitrogen intake at 24 weeks. Our exploratory outcome is muscle mass as measured by D₃-creatine dilution at 24 weeks.

ENROLLMENT AND WITHDRAWAL

Inclusion criteria:

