3-day dietary records-assisted recall – Three consecutive 24hr dietary recalls will be done for 3 days at the beginning of the study. The third recall day will coincide with the 24-hr urines collected for NAE, Ni, and Cr. Both the recalls and urine collections will be done on “normal days” so as to be most representative of the participant’s normal diet pattern. Having 24-hr recalls on the day of the 24-hr urine collections will enable us to link specific foods to daily dietary protein intake and NAE. This diet information will also enable us to adjust our 24-hr UNI measurements for nitrogen intake, and thereby refine the assessment of UNi as a surrogate for protein intake and muscle catabolism at end of study following unblinding. Recalls will also be conducted on weeks 6, 12, 18 and Final Day 2 to track protein intake and NAE throughout the study. 24-hr recalls were used in NHANES, and this will allow us to compare intakes of our participants to national averages. Subjects will be given detailed instructions and measuring aids (a measuring cup, spoons, a ruler and a Food Amounts Booklet) and asked to record everything they eat and drink. They will report what they have consumed to a trained diet technician each day. The 1st recall will highlight what level of food intake detail will be needed to report for the remaining recall days. The dietary interview training is adapted from the 24-hr recall protocol used by the Nutrition Coordinating Center, Minn, MN, <http://www.ncc.umn.edu/index.html>. It is recognized that having to write food items down may alter what participants choose to eat; however, this approach with frequent contact and coaching is likely to give more accurate intake information in our study population than the feasible alternatives, including diet records which do not involve daily staff interaction. The food lists will be coded and analyzed with use of the Minnesota database (NDSR software version 2018, developed by the Nutrition Coordinating Center, U. of Minn., Minn, MN). From this we will attain specific information on food group and nutrient intake, as well as protein nitrogen intake.

Dual energy x-ray absorptiometry (DXA) scans for lean tissue mass

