This proposal involves the participation of human volunteers in a 2x2 factorial design, double-blind, randomized, placebo-controlled study. Participants take an added whey protein packet to achieve a 1.5 g/kg/d protein intake or isocaloric placebo daily with meals and either a KHCO_3 81 mmol/d supplement or a matching placebo daily over a 24-wk period to assess changes in lower extremity muscle power, endurance, handgrip, physical performance, lean and muscle mass, and 24-h UNi excretion. Participants agree to attend up to 9 intrastudy visits (Screening, Enrollment, Baseline, week 1 if on certain medications ONLY, week 6, week 12, week 18, Final Day 1 and 2). These visits will involve (1) a blood draw (Baseline, week 1, week 6, and Final Day 2), (2) return of a 24h urine collection (Baseline and Final Day 2), (3) second fasting urine sample (Baseline and Final Day 1 and 2), (4) double leg press power testing, knee extensor strength testing (Baseline week 12, and Final Day 2), (5) diet recall interviews in person (Baseline, week 6, week 12, week 18, and Final Day 2), (6) hand grip, modified SPPB test, and whole body DXA scan for body composition analysis (Baseline and Final Day 2), and (7) physical activity and medical history questionnaires (Baseline and Final Day 2). Up to 300 men and women age 65 years and over will be screened to attain 120 completers. Participants will be generally healthy and will continue their usual diet and activity level. We will include participants on ≤ 0.8 g/kg/d of dietary protein and are underactive. The study will be conducted at the Jean Mayer USDA HNRCA at Tufts University.

Sources of Materials

At the screening visit, records will be made of the response to screening questionnaires, medical history and physical examination, electrocardiogram, and laboratory results. Daily dietary protein at baseline will be confirmed. Daily physical activity will be assessed. During the course of the study, additional data in the form of records from visits, responses to questionnaires, and testing procedures will be obtained.

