- Health ABC-PPB score at 24 weeks
- 24hr urinary nitrogen excretion

Exploratory:

- muscle mass as measured by D₃-creatine dilution at 24 weeks

b. Analysis methods

Summary statistics. For each outcome, we first will report summary statistics at each timepoint for whey protein vs. no whey protein and for KHCO₃ vs. no KHCO₃. We will then report summary statistics in each of the four cells of the 2x2 design. We also will create box plots that display the distribution of the data at each time point for each comparison.

Primary Outcome. Primary analyses of the primary outcome will be performed on the ITT sample based on an ANCOVA comparing 24-week leg power with fixed effects for intervention groups and further adjustment for leg power at baseline, age and sex. Moreover, the effect of each intervention will be adjusted for the other intervention. Type III sum-of-squares will be used to test significance of each intervention. Least squares mean difference between intervention groups, and 95% confidence intervals, based on the fitted linear models will be reported.

Table 2: Presentation of the results of the primary analyses

	Whey protein	No whey protein	KHCO ₃	no KHCO ₃
Leg power, mean (SD)	xx.x (xx.x)	xx.x (xx.x)	xx.x (xx.x)	xx.x (xx.x)
LS mean difference (95% CI)*		-xx.xx (-xx.x to -xx.x)		-xx.xx (-xx.x to -xx.x)
p value		xxx		Xxx

*adjusted for sex, age, leg power at baseline, and factorial design

Secondary analyses and secondary outcomes.

- We also will conduct factorial analyses of all secondary outcomes by using similar analytic approach to the primary outcome.
- In addition of ANCOVA analyses, we will fit longitudinal model based on all repeated measurements of the outcome, i.e., a linear model with 12-week and 24-week measurements as outcome observations and fixed effects for the intervention group, time treated as categorical, intervention group by time interaction, baseline measure, baseline measure by time interaction, and sex. The corresponding treatment effect measure is the between-group difference in the slopes of the mean responses. Restricted maximum likelihood estimation will be used with the Newton–Raphson algorithm. An unstructured covariance matrix will be used to model the variance-covariance matrix for random intercept and random slope. In the case of nonconvergence with UN, a toeplitz covariance matrix will be used. In the case of nonconvergence with TOEP, an autoregressive covariance matrix [AR (1)] will be used.

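### The SAP leaves out the protocol's nitrogen-intake adjustment of 24-h urinary nitrogen, so its whey contrast as written would mainly reflect packet nitrogen

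*SAP*

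**What the plan says.** Protocol, opening summary: the secondary outcome is "24-hr urinary nitrogen excretion adjusted for nitrogen intake at 24 weeks". Protocol, Objectives and Endpoints: "24-h urinary nitrogen excretion adjusted for nitrogen intake at 24 weeks".

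Protocol, 3-day dietary records-assisted recall, gives the data source: "This diet information will also enable us to adjust our 24-hr UNI measurements for nitrogen intake". The recall is matched to the urine-collection day, and the adjustment is placed at the end of the study, after unblinding.

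The protocol is not uniform. Its Secondary Aims say only "2e) 24h UNi excretion", and Human Subjects Involvement says "lean and muscle mass, and 24-h UNi excretion".

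SAP 7.a lists "24hr urinary nitrogen excretion" with no adjustment and no timepoint, and SAP 3.b does the same. SAP 7.b analyses secondary outcomes in a similar way to the primary outcome, whose model has the two interventions, the baseline value, age and sex. Nitrogen intake is in no SAP model.

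UNi also serves as an objective adherence measure (SAP 5.b), and the protocol's Retention section ties that use to whey.

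**The concern.** The whey packets contain nitrogen, and the comparator is maltodextrin, which the protocol describes as a starch. Most absorbed nitrogen that is not retained leaves in the urine, so UNi should rise in the whey arms even if muscle is unchanged. The protocol expects this: its Study Rationale reports from the pilot "the rise in UNi that accompanied a higher protein intake". That is why UNi works as an adherence marker, and why it cannot serve, without adjustment, as evidence on muscle breakdown for the whey comparison.

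The direction matters. The Study Rationale calls UNi a marker of muscle breakdown, so a rise caused by the packets could be read as whey promoting catabolism. The SAP would report it as a tested secondary outcome at the 0.05 level, with no note that the same variable is the adherence marker.

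**Working it through.** **Inputs from the documents.** Packets hold 15, 20 or 25 g of whey protein, one per meal (Study interventions). An evening packet is skipped around the final visits (procedures table, footnote j), so two or three packets may fall in the urine day. The test is two-sided at 0.05, with 60 vs 60 per margin (SAP 4.c). The ANCOVA has six parameters, so df = 120 - 6 = 114. The documents size the trial on leg power only. There is no UNi effect or SD to reproduce.

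**Assumptions not in the documents.** 6.25 g protein per g N; 50-90% of packet nitrogen recovered in urine; residual SD of UNi 2-4 g N/d; food protein unchanged; no nitrogen in the placebo packet; no muscle effect.

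**Step 1, packet nitrogen.** Per packet: 15/6.25 = 2.4, 20/6.25 = 3.2, 25/6.25 = 4.0 g N. Two packets give 4.8, 6.4 or 8.0 g N/d; three give 7.2, 9.6 or 12.0 g N/d.

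**Step 2, whey contrast with no muscle effect and full adherence.** Packet N x recovery: from 4.8 x 0.5 = 2.4 to 12.0 x 0.9 = 10.8 g N/d.

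**Step 3, comparison with a muscle effect.** Retaining 0.5-2 kg of lean tissue over 168 days, at an assumed 20% protein, is 500 x 0.20/6.25/168 = 0.10 to 2000 x 0.20/6.25/168 = 0.38 g N/d. Even the larger figure is 0.38/2.4 = 16% of the smallest packet contrast. Hence the contrast reflects mainly packets.

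**Step 4, chance of p<=0.05.** SE = SD x sqrt(2/60) = 0.365 (SD 2), 0.730 (SD 4), 1.095 (SD 6). Power is from the noncentral t with 114 df. The grid has 2 packet counts x 3 packet sizes x recovery 0.5, 0.7, 0.9 x SD 2, 4 = 36 combinations. The least favourable is two 15 g packets, 50% recovery, SD 4.

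| Adherence | Lowest | Next lowest | At or above 90% |
|---|---|---|---|
| 100% | 0.903 | 0.991 | 36 of 36 |
| 80% | 0.741 | 0.935 | 35 of 36 |
| 75% (per-protocol cut-off, SAP 5.c) | 0.686 | 0.903 | 35 of 36 |

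At SD 6, outside the assumed range, the least favourable case is 0.584 with full adherence and 0.371 at 75%.

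**Step 5, how far adjustment helps.** Two forms were examined.
- *Subtracting recovery x intake.* An error of 0.2 in the recovery value leaves 0.2 x 4.8 = 0.96 to 0.2 x 12.0 = 2.4 g N/d. The chance of p<=0.05 is then 74% (SD 2) or 26% (SD 4) at 0.96, and over 99% or 90% at 2.4.
- *Recall intake as a covariate.* Ignoring the baseline term, the part left is about recovery x packet N x e²/(h² + e²), where h is the within-arm SD of habitual intake and e the SD of recall error. For two 15 g packets at 70% recovery the raw contrast is 4.8 x 0.7 = 3.36. With h = 1.5, e = 1.5 or 3 leaves 1.68 or 2.69. With h = 3, it leaves 0.67 or 1.68. These SDs are also assumptions.

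Both forms reduce the packet component. Neither removes it reliably, and these figures do not establish that one is better.

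**The case against.** The SAP says that it is to be used with the protocol and does not replace it. It nowhere calls UNi unadjusted, and a similar approach need not mean an identical covariate list. A reader might infer that the investigators decided to drop the adjustment. The documents do not support that: the SAP is silent, and the protocol statements stand. But SAP 1 also undertakes to give analysts clear specifications, and an analyst who followed 3.b, 7.a and 7.b would fit no intake term.

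A reader might also infer that the protocol gives no guidance on the adjustment. It does: the source, the matching of days and the timing are stated. What both documents lack is the model form and a rule for counting packet nitrogen. The missing SAP timepoint is minor, since the only follow-up urine is at the final visit.

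The magnitude rests on recovery and SD values from outside the documents, and on stable food protein, which is counselled but not guaranteed. That objection stands, which is why the SD 6 and lower-adherence results are shown.

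Finally, the authors plainly know that UNi tracks protein intake, and this is one comparison in one secondary outcome. Both points are fair. They limit the harm but do not supply the missing specification.

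**Conclusion.** The point holds. The SAP omits an adjustment that both protocol outcome statements include, and without it the whey contrast would mainly reflect packet nitrogen. Under the stated assumptions with full adherence, a null muscle effect would still give p<=0.05 with a chance of 90% or more; the figure depends on the assumed SD and falls to 58% in the least favourable case at SD 6.

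Three stronger readings are not supported. First, a reader might see false support for whey, because SAP 5.a calls secondary analyses supporting. That word describes their rank, and the likely misreading runs the other way, as catabolism. Second, the KHCO3 comparison is not biased in this way, because whey allocation is balanced across it by randomisation and is in the model. The primary outcome does not use UNi. Third, the documents do not show one adjustment to be correct. In particular, they give no recovery value to subtract.

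**What to change.** 1. In SAP 3.b and 7.a, use the protocol's definition, "24-h urinary nitrogen excretion adjusted for nitrogen intake at 24 weeks", and reconcile the protocol's aim 2e and Human Subjects Involvement with it.
2. State in the SAP that, for the whey comparison, unadjusted UNi is an adherence measure and not evidence on muscle breakdown. It may stay as an outcome for KHCO3.
3. Before outcomes are examined by group, pre-specify the form of the adjustment and an intake source that includes packet nitrogen once. Participants are "asked to record everything they eat and drink", so the rule should say whether the recall already holds the packets. The plan does not propose adding packet diaries to the recall; the rule only needs to settle the matter. Add a sensitivity analysis for the assumed recovery or for recall error, according to the form chosen. The team should choose and justify the form.

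The cost is a little SAP text and one derived variable or covariate; the recalls, packet diaries and urine are already collected. The downside is that the adjustment reduces the packet component without removing it, so the adjusted whey result should be interpreted with that limit stated.
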